## 7.1.1 Screening procedures

### 7.1.1.1 Screening

Prior to performing any screening procedures, the patient must have signed and dated the informed consent document. The investigator is obliged to give the patient thorough information about the study and the study related assessments and she should be given ample time to consider her participation. If a patient is unable to read, an impartial witness should present during the entire informed consent discussion. The original signed informed consent should be kept in the patient's source records and a photocopy of the signed consent should be provided to the patient.

[figure not shown]
For details on the screening assessments please refer to [Table 7-1](#). The investigator or designee must ensure that only patients who meet all of eligibility criteria are offered enrollment on the study. All data for the Inclusion/Exclusion criteria must be verifiable in the patient's source document.

In case the patient does not fulfill all eligibility criteria, the patient will be a screening failure. Re-screening of patients is only allowed once per patient within 28 days of the screening period. In the case of re-screening, the original patient number assigned to the patient will be used and the patient will be identified with the number throughout her entire participation in the study.

Patient eligibility will be checked by the Sponsor once all screening procedures are completed. The eligibility checklist form will be sent from the site to the Sponsor either via fax or email for evaluation. Upon confirmation of eligibility (Key criteria), the Sponsor will return the signed eligibility checklist via fax or email to the site. The investigator site will then be allowed to proceed with the enrollment of the patient into the trial, providing that all other Inclusion/Exclusion criteria are met.

Screening assessments must be done to confirm eligibility prior to the first dose of study drug. Laboratory baseline assessments (including hematology, chemistry, coagulation, and urinalysis), physical examination including performance status, ECG, height and weight must be performed within 28 days prior to first dose of study treatment. Radiological screening assessments performed within 28 days of baseline visit can be used for both study eligibility and baseline assessments. Screening evaluations performed  $\leq 7$  days before the date of the first dose of study treatment for all laboratory assessments and ECOG performance status can be used as baseline evaluations (i.e., need not be performed on Cycle 1 Day 1). Patients with potassium, sodium and/or calcium levels that are below the LLN at screening must have their potassium, sodium and/or calcium replenished through supplementation and the levels must be within normal limits prior to the first dose of study drug.

Information from procedures that may have been previously performed as part of the patient's routine disease care (prior to enrolling the trial) is allowed to be used to satisfy inclusion criteria as long as the procedures were performed within 28 days of study drug start.

### **7.1.1.2 Information to be collected on screening failures**

Patients who sign an informed consent but fail to be started on treatment for any reason will be considered a screen failure. The reason for not being started on treatment will be entered on the Screening Failure Log. The Demography CRF page must also be completed for all screen failures. No other data will be entered into the clinical database for subjects who are screen failures, unless the subject experienced a Serious Adverse Event during the Screening Phase (see [Section 8](#) for SAE reporting details).

### **7.1.1.3 Hepatitis screening/baseline**

In cancer patients with hepatitis B, whether carriers or in chronic state, use of antivirals during anticancer therapy has been shown to reduce the risk of hepatitis B virus (HBV) reactivation and associated HBV morbidity and mortality ([Loomba et al 2008](#)).

#### **7.1.1.3.1 Screening for hepatitis B**

Prior to starting trial therapy, the following three categories of patients should be tested for hepatitis B viral load and serologic markers, that is, HBV-DNA, HBsAg, HBs Ab, and HBc Ab:

1. All patients who currently live in (or have lived in) Asia, Africa, Central and South America, Eastern Europe, Spain, Portugal and Greece.  
(<http://nc.cdc.gov/travel/yellowbook/2010/chapter-2/hepatitis-b.aspx#849> )
2. Patients with any of the following risk factors:
  - known or suspected past hepatitis B infection,
  - blood transfusion(s) prior to 1990,
  - current or prior IV drug users,
  - current or prior dialysis,
  - household contact with hepatitis B infected patient(s),
  - current or prior high-risk sexual activity,
  - body piercing or tattoos,
  - mother known to have hepatitis B
  - history suggestive of hepatitis B infection, e.g., dark urine, jaundice, right upper quadrant pain.
3. Additional patients at the discretion of the investigator

The management guidelines, in [Section 6.2.2.3](#), are provided according to the results of the baseline assessment of viral load and serological markers for hepatitis B.

#### **7.1.1.3.2 Screening for hepatitis C**

Patients with any of the following risk factors for hepatitis C should be tested using quantitative RNA-PCR

- known or suspected past hepatitis C infection (including patients with past interferon ‘curative’ treatment),
- blood transfusions prior to 1990,

- current or prior IV drug users,
- current or prior dialysis,
- household contact of hepatitis C infected patient(s),
- current or prior high-risk sexual activity,
- body piercing or tattoos,

At the discretion of the investigator, additional patients may also be tested for hepatitis C.

The management guidelines, in [Section 6.2.2.3](#), are provided according to the results of the baseline assessment of hepatitis C viral load.

[figure not shown]
#### **7.1.1.4 Patient demographics and other baseline characteristics**

The following patient demographic and baseline characteristics will be collected on the eCRF:

- General demography including age, gender, race, ethnic origin
- Medical history/current medical conditions (including prior and concomitant medications and prior antineoplastic therapies)
- History and current disease status (including staging, diagnosis information, hormonal receptor and HER2 status, previous anticancer treatments and sites of disease). The following information must be collected for all previous anticancer therapies: start date, end date, setting (neoadjuvant vs. adjuvant vs. therapeutic), best response, reason for treatment discontinuation.
- Physical/neurological examination, weight and height
- Vital signs including sitting blood pressure, pulse and temperature
- ECOG performance status
- ECG
- Safety laboratory assessments: chemistry, hematology, urinalysis coagulation
- HBV testing: prior to enrollment, the categories of patients listed in [Section 7.1.1.3](#) should be tested for hepatitis B serologic markers and viral load: HBV-DNA HBsAg, HBcAb, and HBsAb. HBVDNA monitoring should be done depending on results from serologic markers and viral load as listed in [Table 6-6](#).
- HCV testing: patients with hepatitis C risk factors and additional patients at the discretion of the investigator should be testing for HCV RNA-PCR test at baseline. For a list of hepatitis C risk factors, refer to [Section 7.1.1.3](#). Follow-up testing will be performed, as per [Section 6.2.2.3](#), only if the patient has a history or is positive at baseline or both.
- Bone scan or skeletal survey
- Radiological tumor assessment (CT or MRI for chest, abdomen, pelvis, brain and bone scan or skeletal survey); positive areas on bone scans must be assessed by X-ray, CT scan with bone windows or MRI

#### **7.1.2 Treatment period**

Patients will start study treatment at treatment 1 day 1 (cycle 1 day 1) and continue to be treated per protocol until documentation of disease progression or any other reason for which

the patient may be discontinued (refer to [Section 7.1.5](#)). However, study treatment may prematurely be discontinued for other reasons as well.

Compliance will be assessed by the investigator and/or study personnel at each visit using pill counts and/or information provided by the patient or caregiver. This information should be captured in the source document at each visit for all study drugs (everolimus, letrozole and exemestane).

To accurately record the administration of study treatments, the following information must be recorded on the DAR page of the eCRF throughout the study:

- Actual total dose administered
- Regimen
- Start/End date of drug administration
- Dose change/delay and reason for such

### **7.1.3 Second line treatment**

Following disease progression in the first line setting, patients will be offered everolimus in combination with exemestane during the Core Phase, during the Extension Phase these patients will be discontinued from the study. Patients who discontinued first line treatment due to reasons other than disease progression are not eligible for second line treatment.

Informed consent will not be repeated for patients moving into the second line treatment period. However, specified inclusion / exclusion criteria must be re-examined (see [Section 5.1](#)) and collected on the eCRF.

At the determination of documented disease progression (e.g., image scan that determined the disease progression) in the first line treatment, the patient must begin second line treatment within 28 days.

A complete schedule of evaluations required for the second line treatment period are provided in [Table 7-2](#).

The procedures for patients receiving second line treatment will proceed as follows:

- Re-examination of specified inclusion/exclusion criteria, see [Section 5.1](#).
- ECOG Status
- Current concomitant medications
- Safety laboratory assessments: chemistry, hematology, urinalysis, coagulation
- HBV and HCV testing and monitoring should be continued only for those patients identified during enrollment on first line treatment. Testing should be performed as per [Section 6.2.2.3](#).
- Tumor evaluations will follow the same schedule used in the first line treatment period. If the end of treatment tumor evaluations from the first line treatment period that lead to documentation of disease progression is <28 days prior to starting the second line treatment medication, then the end of treatment tumor evaluations from the first line will serve as Cycle 101 day 1 tumor evaluations for second line treatment period

- All continuing concomitant medications from the first line treatment period will be followed into the second line treatment period and will be recorded on the Concomitant Medications eCRF
- Treatment with everolimus and exemestane in the second line period continues until documented disease progression or any other reason for which the patient may be discontinued (refer to [Section 7.1.5](#))
- When patients discontinue the second line treatment for any reason, an end of treatment visit following discontinuation of the second line medication will be performed. The 28 day follow up visit will also be performed to check on continuing AEs/SAEs or any new AEs/SAEs that may have occurred
- The first dose of open-label second line study medication begins at Cycle 101 day 1

#### **7.1.4 Extension Phase**

Following the overall survival cut-off (24 months post LPFV) and approval of Amendment 5, patients continuing to derive benefit from everolimus will be transitioned to an Extension Phase until disease progression or any other reason for which the patient may be discontinued (refer to [Section 7.1.5](#)).

Patients will be re-consented prior to starting the Extension Phase.

Patients must return to the study center on a quarterly basis (12 weeks  $\pm$  1 week) for resupply of medication at which time drug dispensing information and adverse event information will be collected.

A complete schedule of evaluations required for the Extension Phase is provided in [Table 7-3](#).

The procedures for patients entering the Extension Phase will proceed as follows:

- Safety laboratory assessments: chemistry, hematology, urinalysis, coagulation will be done as clinically indicated
- HBV and HCV testing and monitoring should be continued only for those patients identified during enrollment on first line treatment. Testing should be performed as per [Section 6.2.2.3](#).
- Treatment with everolimus and letrozole (1st line) or everolimus and exemestane (2nd line) until lack of clinical benefit as assessed by Investigator at the site or any other reason for which the patient may be discontinued (refer to [Section 7.1.5](#)) Patients entering the Extension Phase on 1st line treatment and deemed to no longer be clinically benefiting will not be offered 2nd line treatment in the context of this study)
- At every quarterly visit, the investigator is required to confirm that the patient continues to have clinical benefit and may continue receiving study treatment. Although formal assessment of efficacy is not required during the Extension Phase, confirmation of continued treatment benefit as per standard of care is mandatory.
- When patients discontinue the first or second line treatment for any reason, an end of treatment visit following discontinuation of the medication will be performed. The 28 day follow up visit will also be performed to check on continuing AEs/SAEs or any new AEs/SAEs that may have occurred

### **7.1.5 End of treatment visit including study completion and premature withdrawal**

At the time patients discontinue study treatment (in the first line treatment or, if applicable, second line treatment and Extension Phase), a visit should be scheduled as soon as possible (within 2 weeks), at which time all of the assessments listed for the End of Treatment (EOT) visit will be performed. An End of Treatment eCRF page should be completed separately for both first and second line treatment for the core study phase, and an End of Treatment eCRF for the Extension Phase should be completed for those subjects ending treatment while in the Extension Phase. The EOT eCRF will provide the date and reason for stopping the study treatment.

[figure not shown]
If patients refuse to return for an end of treatment visit or are unable to do so, every effort should be made to contact them or a knowledgeable informant by telephone to determine the primary reason for premature withdrawal from the study and record this information on the End of Treatment eCRF page.

Patients may voluntarily withdraw from the study or be dropped from it at the discretion of the investigator at any time. Patients may be withdrawn from the study if any of the following occur:

- Pregnancy
- Discovery of patient ineligibility
- Protocol violation or errors in treatment compliance [study treatment, other prescribed or non-prescribed medications]
- Missed/unscheduled/off-schedule/incomplete/incorrect assessments
- Adverse events (including abnormal laboratory value, abnormal test procedure result)
- Unacceptable toxicity
- Subject withdrew consent
- Lost to follow up
- Administrative problems
- Death
- New cancer therapy
- Disease progression
- Treatment duration completed as per protocol
- Discontinuation of everolimus development by Novartis

At a minimum, all patients who discontinue study treatment for any reason, including those who refuse to return for a final visit, will be contacted for safety evaluations during the 28 days following the last dose of study treatment. If patients begin second line treatment < 28 days after completion of first line treatment, safety evaluations should continue until second line treatment begins.

All patients who discontinue treatment due to disease progression should be scheduled for a visit as soon as possible (within 2 weeks), at which time all of the assessments listed for the End of Treatment visit will be performed. After the 28-day safety follow-up visit, the patient

will begin the survival follow up period. At the start of new antineoplastic therapy, the patient will complete the Study Evaluation Completion eCRF.

If a patient discontinues treatment for reasons other than progression of disease according to RECIST 1.0 (see [Appendix 2](#)) tumor imaging evaluations should be performed at the End of Treatment visit (along with EOT assessments) unless the last tumor imaging evaluation was performed  $\leq$  4 weeks earlier. This does not apply to the Extension Phase, once the patient enters the extension, tumor imaging is no longer required per the study schedule.

All information on the start of a new antineoplastic therapy should be obtained and must be recorded in the Antineoplastic Therapies Since Discontinuation of Study Drug eCRF. If patients refuse to return for these visits or are unable to do so, every effort should be made to contact them or a knowledgeable informant by telephone to determine the patient's disease status or any start of new antineoplastic therapy. The Study Evaluation Completion eCRF page should be completed upon the patient's completion of the study.

### **7.1.6 Follow up period**

All patients must have safety evaluations for 28 days after the last dose of study treatment.

Patients lost to follow up should be recorded as such on the eCRF. For patients who are lost to follow up, the investigator should show "due diligence" by documenting in the source documents steps taken to contact the patient, e.g., dates of telephone calls, registered letters, etc. The investigator must determine the primary reason for a patient's premature withdrawal from the study and record this information on the End of Treatment or Study Evaluation Completion eCRF as applicable.

#### **7.1.6.1 Study evaluation completion**

The study evaluation completion eCRF will be completed once all study evaluations are completed and patients are only being followed for survival (if applicable).

#### **7.1.6.2 Survival follow up**

All patients who discontinued study treatment, have started a new antineoplastic therapy, and/or are no longer followed radiologically will be contacted (via telephone) for survival information every 12 weeks from the patient's last visit (which can be the safety follow up visit), until death, lost to follow up or withdrawal of consent. The investigator or his designee will collect this survival information and any additional antineoplastic therapies for all patients until the final survival analysis.

Patients who withdraw consent from participation in study should be asked to consent for survival follow up. If applicable, information regarding the death should be captured in the eCRF.

Patients completing the Extension Phase will not be followed for survival.

## 7.2 Assessment types

### 7.2.1 Efficacy assessments

#### Core Phase

Patients should have either at least one lesion that can be measured as per RECIST 1.0 criteria OR have bone lesions: lytic or mixed (lytic + sclerotic) in the absence of measurable disease as defined above.

For patients with measurable disease at baseline (as per RECIST 1.0 criteria), efficacy (overall tumor response and progression) will be evaluated every 8 weeks (+/- 1 week) during the Core Phase according to the RECIST 1.0 criteria. If an initial observation of response is made, a confirmation scan (or photography for measurable skin lesions) should be obtained at least 4 weeks after the initial observation. All patients being discontinued from the study for disease progression must have their progression documented using the criteria specified in [Appendix 2](#). All patients who discontinue study treatment for any reason (i.e., an adverse event, administrative reasons etc) other than disease progression or consent withdrawal will continue to have tumor assessments per the schedule during the Core Phase until disease progression or until new anti-cancer therapy is initiated.

All primary and secondary endpoints based on radiological (and photographic when applicable) assessments of tumor burden will be derived using the local (treating centers) radiologist's / investigator's assessment.

A bone scan or a skeletal survey should be performed at baseline for all patients within 28 days of enrollment. Any abnormalities (i.e., hotspots) identified on the bone scan must be confirmed by X-ray, CT scan with bone windows or MRI. Bone lesions identified at baseline should follow the same assessment schedule as for measurable lesions. Additional bone scans or skeletal surveys should be performed if clinically indicated. Abnormalities found on subsequent bone scans must also be confirmed by X-ray, CT scan or MRI.

The same method of assessment and the same technique should be used to characterize each identified and reported lesion at baseline for each study tumor assessment after start of study treatment.

If possible, each center should have a designated radiologist responsible for the interpretation of CT or MRI scans and the evaluation according to RECIST 1.0 criteria (see [Appendix 2](#) for details). The same radiologist/physician should perform the evaluation for the entire duration of the study. All radiology evaluations will be performed initially by the local radiologist.

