### **10.4.1 Variable**

The primary efficacy endpoint in this study is PFS, defined as the time from the date of enrollment to the date of first documented progression or death due to any cause. If a patient has not had an event, PFS will be censored at the date of the last adequate tumor assessment. See RECIST, [Appendix 2](#). The primary efficacy endpoint will be assessed as per local radiological assessment.

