### **10.4.3 Handling of missing values/censoring/discontinuations**

In this study the primary analysis of PFS for first line treatment will be performed 12 months after the last patient's recruitment. The analysis of PFS for second line treatment will be performed 6 months later (18 months after the last patient's recruitment) provided that the number of patients in second line treatment is adequate for a reliable PFS analysis. Otherwise, this analysis will be performed 24 months after the last patient's recruitment. For the analyses, PFS will be censored on the date of last adequate tumor assessment, if no PFS event is observed before the cut-off date or before the date a new anti-neoplastic therapy or another investigational treatment for cancer is started, whichever occurs earlier. If a PFS event is observed after two or more missing or non-adequate tumor assessments, then the date of progression will be censored at the latest occurring evaluable tumor assessment. If a PFS event is observed after a single missing or non-evaluable tumor assessment, the actual date of event will be used.

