**Situations C (C1 and C2): Progression or death after one or more missing assessments:**

The primary analysis is usually using options (1) for situations C1 and C2, i.e.

- (C1) taking the actual progression or death date, in the case of only one missing assessment.
- (C2) censoring at the date of the last adequate assessment, in the case of two or more consecutive missing assessments.

In the case of two or missing assessments (situation C2), option (3) may be considered jointly with option (1) in situation C1 as sensitivity analysis. A variant of this sensitivity analysis consists of backdating the date of event to the next scheduled assessment as proposed with option (2) in situations C1 and C2.

**Situation E: Treatment discontinuation due to ‘Disease progression’ without documented progression:** By default, option (1) is used for situation E as patients without documented PD should be followed for progression after discontinuation of treatment. However, option (2) may be used as sensitivity analysis. If progression is claimed based on clinical deterioration instead of tumor assessment by e.g. CT-scan, option (2) may be used for indications with high early progression rate or difficulties to assess the tumor due to clinical deterioration.

**Situation F: New cancer therapy given:** the handling of this situation must be specified in detail in the protocol. However, option (1), i.e. censoring at last adequate assessment may be used as a default in this case.

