#### **14.2.21 Treatment and study completion CRFs**

If study drug is discontinued, the **treatment completion page** is to be completed with a visit date reflecting the date the discontinuation decision was made, and with the 'Last known date subject took study drug' and one of the following reasons:

- Adverse event(s)
- Abnormal laboratory value(s)
- Abnormal test procedure results(s)
- Protocol violation
- Subject withdrew consent
- Lost to follow-up
- Administrative problems
- Death
- Disease progression
- Treatment duration completed as per protocol (optional, to be used if only a fixed number of cycles is given)

For reasons other than progression (and death) it should be checked if this was not in fact progression (especially reasons Adverse Events, Abnormal laboratory value (s), Abnormal test procedure result and subject withdrew consent). Also it should be checked if patient withdrew consent because of safety issues, in which case reasons Adverse Events, Abnormal laboratory value (s), Abnormal test procedure result should be used.

All patients who discontinued study drug for reasons other than documented progression, death or lost to follow-up will be followed for progression thereafter (patients who withdrew consent might not be followed with regular tumor assessments at the study site, but should ideally be followed until progression outside the study site). Ideally, all patients who discontinued study drug for progression without documented progression will still be followed with regular tumor assessments (e.g. in case of central radiology review). During that evaluation period, usually only tumor measurements (and/or response status) and survival data are collected. In some protocols, the subsequent anti-cancer therapies may also be recorded.

At the end of the study evaluation period, the **study evaluation completion page** is filled out with the following options:

- Subject withdrew consent
- Lost to follow-up

- Administrative problems (when follow-up for progression has met protocol required events, e.g. follow-up stopped at certain number of events or certain time)
- Death
- New cancer therapy (optional, to be used when follow-up for progression is stopped in this case)
- Disease progression

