#### **14.2.22 Medical validation of programmed overall lesion response**

As RECIST is very strict regarding measurement methods (i.e. any assessment with more or less sensitive method than the one used to assess the lesion at baseline is considered UNK) and not available evaluations (i.e. if any target or non-target lesion was not evaluated the whole overall lesion response is UNK unless remaining lesions qualified for PD), these UNK assessments may be re-evaluated by clinicians at Novartis or external experts. In addition, data review reports will be available to identify assessments for which the investigators' opinion does not match the programmed calculated response based on RECIST criteria. This may be queried for clarification. However, the investigator response assessment will never be overruled.

If Novartis elect to invalidate an evaluation of overall lesion response upon internal or external review of the data, the calculated overall lesion response at that specific assessment is to be kept in a dataset. This must be clearly documented in the RAP documentation and agreed before database lock. This dataset should be created and stored as part of the 'raw' data.

Any discontinuation due to 'Disease progression' without documentation of progression by RECIST criteria should be carefully reviewed. Only patients with documented deterioration of symptoms indicative of progression of disease should have this reason for discontinuation of treatment or study evaluation.

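### Sections 7.2.1 and 7.1.5 conflict with Appendix 2 on scanning patients who stop for progression not documented by RECIST, which leaves room for informative censoring of PFS

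*Protocol*

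**What the plan says.** **Endpoint.** Section 10.4.1 gives the primary endpoint as a time "defined as the time from the date of enrollment to the date of first documented progression or death due to any cause". Section 10.4.3 says: "PFS will be censored on the date of last adequate tumor assessment, if no PFS event is observed before the cut-off date". The start of new anti-cancer therapy is a second limit. An event that follows two or more missing or non-adequate assessments is also censored.

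**Main-text follow-up.** Section 7.2.1 governs scans after treatment stops. It covers patients whose stop had a cause "other than disease progression or consent withdrawal will continue to have tumor assessments per the schedule during the Core Phase until disease progression", with new therapy as the other end point. Section 7.1.5 begins a paragraph with "All patients who discontinue treatment due to disease progression should be scheduled for a visit as soon as possible" and takes these patients through the end-of-treatment (EOT) and 28-day visits into survival follow-up. Neither passage limits 'disease progression' to documented progression.

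**Appendix 2.** In Table 14-5, situation E is a stop for progression that was not documented. Its default, option 1, ignores the claim. Section 14.2.18 justifies this default "as patients without documented PD should be followed for progression after discontinuation of treatment". Section 14.2.21 says that everyone who stops for a reason other than documented progression, death or loss to follow-up will be followed. For this particular group it adds: "Ideally, all patients who discontinued study drug for progression without documented progression will still be followed with regular tumor assessments". Section 14.2.22 states: "Any discontinuation due to 'Disease progression' without documentation of progression by RECIST criteria should be carefully reviewed". It allows the stop reason where symptomatic deterioration is documented.

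**The concern.** The default in situation E is reasonable only if the patient stays on the scan schedule, so that a later scan or death can supply the event. The main text, taken at its word, removes that condition.

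Take a patient with stable disease on a scan who worsens clinically 3 weeks later and stops with the reason 'disease progression'. Section 7.1.5 waives the EOT scan when imaging was done within 4 weeks, and the literal 7.2.1 requires no later scan. She is censored at the stable-disease scan. If the unperformed 8-weekly scans count as missing, two have been missed about 16 weeks after that scan, which is about 16 − 3 = 13 weeks after she stopped. A death later than that is censored too, and so is any outcome after new therapy.

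Such censoring happens because the patient is failing, so it can only push the Kaplan-Meier median upward. The trial has one arm, and section 10.8 sets its expected 11 to 14 months beside about 9 months for an aromatase inhibitor alone. No control arm would share the bias. Second-line PFS has the same exposure.

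**Working it through.** **1. Passages side by side.**

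| Place | Who leaves tumour follow-up, or skips the EOT scan |
|---|---|
| 7.2.1, continuing scans | stops for disease progression, unqualified |
| 7.1.5, progression paragraph | stops for disease progression, unqualified: to survival follow-up |
| 7.1.5, next paragraph | EOT scan required unless the stop was RECIST 1.0 progression; waived if imaged within 4 weeks |
| Table 7-1, EOT imaging | only documented PD, loss to follow-up or death exempt; no 4-week waiver |
| 14.2.21, general rule | only documented progression, death or loss to follow-up ends follow-up |
| 14.2.21, undocumented progression | continued assessment, stated as an ideal |

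A patient who stops for undocumented progression fits both 7.1.5 paragraphs. The first sends her to survival follow-up; the second adds at most one scan. The 7.1.5 waiver and Table 7-1 also disagree.

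**2. The plan's own figure.** Inputs from section 10.8: N = 200, 18 months of accrual, 12 further months, 10% lost. I assumed exponential PFS, uniform accrual, and the 10% loss spread exponentially over 30 months.

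- λ = ln 2/12 = 0.05776 and η = −ln(0.9)/30 = 0.00351; their sum is 0.06127.
- d = 200 × (0.05776/0.06127) × [1 − (e^(−0.06127×12) − e^(−0.06127×30))/(0.06127×18)] = 133.8 events.
- 95% CI = 12 × exp(±1.96/√133.8) = 10.13 to 14.22 months.

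This matches the section 10.8 table, and the 11-, 13- and 14-month rows match as well. The table is correct; it serves here only as the scale.

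**3. Upper bound on the bias.** Let f be the share of progressors who stay undocumented, are not followed, and have no countable death. The protocol gives no f, so 5% to 15% is an assumption. If all of them are censored as they fail, the observed hazard is (1 − f) times the true one, and the apparent median is 12/(1 − f).

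| f | Apparent median (months) | Events lost (f × 133.8) |
|---|---|---|
| 0 | 12.0 | 0 |
| 5% | 12/0.95 = 12.6 | 6.7 |
| 10% | 12/0.90 = 13.3 | 13.4 |
| 15% | 12/0.85 = 14.1 | 20.1 |

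**4. Check by simulation.** With 200 patients, 8-weekly scans (±1 week) and 10% loss, the mean Kaplan-Meier median rises by about 0.6, 1.1 and 1.8 months at f = 5%, 10% and 15%. The formula gives rises of 0.6, 1.3 and 2.1. The typical (median) simulated estimate moves in jumps, from 12.9 at f = 0 to 14.5 at 10% and 14.7 at 15%, because events fall on the scan grid. Those jumps should not be read as the bias. If 30% of these patients die early enough to count, the mean rise at 10% falls to about 0.8 months.

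**The case against.** The strongest reply is that 7.2.1 should not be read one sentence at a time. The sentence just before the quoted one says: "All patients being discontinued from the study for disease progression must have their progression documented using the criteria specified in" Appendix 2. Section 6.1.2 ends first-line treatment on RECIST-documented progression, toxicity or withdrawal of consent. Section 7.1.3 ties second-line treatment to documented progression, which gives sites a reason to image. Table 7-1 exempts only documented PD, loss to follow-up and death from the EOT scan, and the general rule in 14.2.21 keeps everyone else in follow-up. On this reading the worked patient results from departures from the plan, not from the plan.

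Much of this stands. A reader might infer that 7.2.1 ends scans for progression whether documented or not, and that median PFS is therefore overstated. The documents do not support that: the first is one literal reading against several contrary passages, and the second needs a share f that the protocol does not state and that could be near zero. The figures above are also ceilings, and even 14.1 months lies inside the plan's own interval of 10.13 to 14.22 at a 12-month median.

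It does not remove the conflict. The preceding sentence concerns patients discontinued from the study, whereas the exemption concerns those who stop study treatment; the glossary separates the two. That sentence also gives no instruction when documentation is lacking. Appendix 2 plainly expects some undocumented stops, and it covers them in Table 14-5, 14.2.21 and 14.2.22. Where it addresses exactly this group, it falls back to an ideal, in material that 14.2.19 introduces as guidance.

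**Conclusion.** The inconsistency is real and touches the primary endpoint. The main text, read literally, releases patients with undocumented progression from the scans that Appendix 2 relies on when it ignores their claimed progression. It permits informative censoring; it does not make it certain.

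The direction is known: any bias raises median PFS. The size is not. At a true median of 12 months the upper bound is 12.6 to 14.1 months for assumed f of 5% to 15%, with no bias at f = 0. This rests on exponential PFS and on every patient counted in f being lost. EOT scans, follow-up under 14.2.21 and early deaths would all reduce it. No figure in section 10.8 is wrong.

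**What to change.** - In 7.2.1, insert the words RECIST 1.0-documented before 'disease progression' in the phrase that exempts patients from continued scans.
- Qualify the 7.1.5 paragraph on stopping due to disease progression in the same way. Patients stopped for undocumented progression then stay on the 8-weekly schedule until documented progression or new therapy.
- Reconcile the 4-week waiver of the EOT scan in 7.1.5 with Table 7-1, which has none.
- Optional: a PFS sensitivity analysis using Table 14-5, situation E option 2, which counts the stop as an event on the discontinuation date. This may sit in the analysis plan, and its absence from the protocol is not a fault.

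The cost is a few words in two sections, a few more scans that are already on the schedule, and possibly a slightly lower reported median.
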